#### 3.3.4.2 Withdrawal of consent to trial participation

Trial participants may withdraw their consent to trial participation at any time without the need to justify the decision.

If a trial participant wants to withdraw consent, the investigator should be involved in the discussion with the trial participant and explain the difference between trial treatment discontinuation and withdrawal of consent to trial participation, as well as explain the options for continued follow-up after trial treatment discontinuation; please see Section 3.3.4.1.

Withdraw of consent is when the trial participant declines any further participation in the clinical trial and is confirmed when the patient meets all of the below:

- Does not want to take trial medication any longer and
- Does not want to continue to come to the site/clinic for protocol scheduled trial visits after treatment discontinuation and
- Does not want to be contacted periodically and
- Does not want to be contacted at the end of the trial and
- Does not provide access to the own health records

If any of these is not met, then it is not a withdrawn of consent.

Page 58 of 177

Proprietary confidential information © 2023 Boehringer Ingelheim International GmbH or one or more of its affiliated companies

# 3.3.4.3 Discontinuation of the trial by the sponsor

Boehringer Ingelheim reserves the right to discontinue the trial overall or at a particular trial site at any time for the following reasons:

- 1. Failure to meet expected enrolment goals overall or at a particular trial site.
- 2. New efficacy or safety information invalidating the earlier positive benefit-risk assessment; please see Section 3.3.4.1.
- 3. Deviations from GCPs, the trial protocol, or the contract impairing the appropriate conduct of the trial.

Further treatment and follow up of trial participants affected will occur as described in Section 3.3.4.1.

The investigator/the trial site will be reimbursed for reasonable expenses incurred in case of trial termination (except in case of the third reason).

Page 59 of 177

Proprietary confidential information © 2023 Boehringer Ingelheim International GmbH or one or more of its affiliated companies

# 4. TREATMENTS

# 4.1 INVESTIGATIONAL TREATMENTS

# 4.1.1 Identity of the investigational medicinal products

Table 4.1.1: 1 Test product spesolimab solution

Substance:	Spesolimab (Spevigo®)
Pharmaceutical formulation:	
Source:	Boehringer Ingelheim Pharma GmbH & Co. KG
Unit strengths:	Spesolimab
Posology:	See Section 3.1.

Table 4.1.1: 2 Test product BI matching placebo solution

agan Ingalhaina Phanna CmhII & Ca VC
a con la colle sina Dhamas Crahill & Co. V.C.
nger Ingelheim Pharma GmbH & Co. KG
etion 3.1.

# Table 4.1.1: 3 Test product spesolimab solution

Substance:	Spesolimab (Spevigo®)
Pharmaceutical formulation:	
Source:	Boehringer Ingelheim Pharma GmbH & Co. KG
Unit strengths:	Spesolimab
Mode of administration:	
Posology:	See Section 3.1 .

Page 60 of 177

Proprietary confidential information © 2023 Boehringer Ingelheim International GmbH or one or more of its affiliated companies

ruste 1:1:1: 1 Test product B1 matering placedo solution	Table 4.1.1: 4	Test product BI matching placebo solution	on
--	----------------	---	----

Substance:	Placebo matching to spesolimab
Pharmaceutical formulation:	
Source:	Boehringer Ingelheim Pharma GmbH & Co. KG
Unit strengths:	
Mode of administration:	
Posology:	See Section 3.1.

# 4.1.2 Selection of doses in the trial and dose modifications

# Part 1 (Phase IIb)

[figure not shown]
The main trial objectives of Part 1 in this trial is provided in Section 2.1.1.

dosing regimens are defined (for details, see Section 3.1 ) in this trial: one middle dosing regimen (middle dose group)
one higher dosing regimen (high dose group); and one lower dosing regimen (low dose group).
Taken together, trial participants randomised to active treatment in
1368-0052 received then starting Those randomised to placebo in 1368-0052 received placebo until Week 10.
Starting and after final evaluation of Study 1368-0052 (EoT visit), the former placebo trial participants
Thereafter all trial participants were continued
Safety for the lower and medium dosing regimen is supported by the safety profile observed in Study

Page 61 of 177

Proprietary confidential information © 2023 Boehringer Ingelheim International GmbH or one or more of its affiliated companies

In the healthy volunteer (HV) study (1368-0002), 6 healthy volunteers were exposed to the highest 20 mg/kg dose. In those 6 trial participants, no serious adverse event (SAE) or adverse event of special interest (AESI) were reported. At PT level, the most frequently reported treatment-emergent AEs (more than 20% of the trial participants who received spesolimab in the MRD part) were nasopharyngitis, headache, and injection site erythema. All AEs resolved by the end of the trial or were followed up sufficiently. No relevant changes were observed in safety laboratory tests, vital signs, and ECGs. Based on these safety findings from the 1368-0002 study, the highest dose planned for the 1368-0098 study can be considered as acceptable.

Page 62 of 177

Proprietary confidential information © 2023 Boehringer Ingelheim International GmbH or one or more of its affiliated companies

# Part 2 (Phase III)

Dose regimens to serve trial objectives of Part 2 (Phase III), defined in Section 2.1.1, will be selected according to Part 1 (Phase IIb) results. Justification of selecting the dose regimens will be clarified in an amended CTP.

# 4.1.3 Method of assigning trial participants to treatment groups

For both Part 1 and Part 2, after the assessment of all in- and exclusion criteria, each eligible trial participant will be randomised to a treatment group at Visit 2 according to a randomisation plan, please see Section 7.4. Randomisation codes will be generated through a validated software and kept blinded to the trial team, sites and trial participants. Access to the codes will be controlled and documented.

An
The investigator will receive all necessary instructions to access the from the sponsor. Detailed functions and procedures will
be documented in the user requirement specifications mutually agreed to by the sponsor and
the

# 4.1.4 Blinding and procedures for unblinding

# 4.1.4.1 Blinding

#### Part 1 (Phase IIb)

Trial participants, investigators, central reviewers, and everyone (except for specified project members [e.g. PK]) involved in trial conduct or with any other interest in this double-blind trial will remain blinded regarding the randomised treatment assignments until the database is declared ready for final analysis according to the sponsor's SOPs.

Further details, regarding the timepoint of unblinding the database for analyses including primary, interim, and final analysis, are documented in the TSAP or logistics plan.

The randomisation codes will be provided to bioanalytics before the last trial participant completed the visit of Phase IIb (Part 1) of the trial to exclude placebo samples from the PK and ADA analysis. Bioanalytics will not disclose the randomisation code or the results of their measurements until the database lock.

For the primary analysis at and interim analysis at a respective team ("shadow team") independent of the main trial team will be formed to conduct the necessary analysis and reporting steps and ensure to maintain the blind and restrict access to the randomisation codes from the main trial team. Details of data transfer, timelines, and involved trial functions during this process will be described in a separate logistics plan which will also specify details on data access.

Page 63 of 177

Proprietary confidential information © 2023 Boehringer Ingelheim International GmbH or one or more of its affiliated companies

# Part 2 (Phase III)

Trial participants, investigators, central reviewers, and everyone involved in trial conduct, trial analysis, or with any other interest in this double-blind trial will remain blinded regarding the randomised treatment assignments until the database is declared ready for analysis according to the sponsor's SOPs. Further details, regarding the timepoint of unblinding the database for analysis, will be documented in the TSAP.

The responsible bioanalyst of the external bioanalytical laboratory will receive the randomisation codes prior to last trial participant completed to allow for the exclusion from the analyses of PK and ADA samples taken from placebo trial participants.

The TBA may receive unblinding data from the external bioanalytical laboratory after the last trial participant completed the last visit but prior to official unblinding of the analysis database at the end of the trial for preparation of data transfer e.g. check file structure prior to data upload and SDTM transformation and bioanalytical report writing. Bioanalytics will not disclose the randomisation code or the results of their measurements until the database lock.

## Part 1 (Phase IIb) and Part 2 (Phase III)

The access to the randomisation code will be kept restricted until its documented release per sponsor SOP.

A fully external DMC will perform an un-blinded safety and efficacy assessment at specified intervals in order to ensure that trial participants are protected from potential harm, please refer to Section 8.7 for further details.

#### 4.1.4.2 Emergency unblinding and breaking the code

Emergency unblinding will be available to the investigator via IXRS and emergency service. It must only be used in an emergency when the identity of the trial drug must be known to the investigator in order to provide appropriate medical treatment or otherwise assure safety of trial participants. The treatment allocation should not be disclosed to the sponsor unless this is explicitly requested. The reason for unblinding must be documented in the source documents and/or appropriate CRF page.

Due to the requirements to report Suspected Unexpected Serious Adverse Reactions (SUSARs), it may be necessary for a representative from BI's Pharmacovigilance group to access the randomisation code for individual trial participants during trial conduct. The access to the code will only be given to authorised PSPV representatives for processing in the Pharmacovigilance database and not be shared further.

# 4.1.5 Drug assignment and administration of doses for each trial participant

Trial participants for Part 1 will be treated with spesolimab or matching placebo as indicated in the Flowchart and Section 3.1. Trial participants for Part 2 treatment schedule will be simplified, based on the results from Part 1 data available when the primary analysis will be conducted. Therefore, the rest of this section applies to study participants in Part 1. This section will be duly amended to include any change applied to drug administration for study participants in Part 2 after the Part 1 primary analysis has been conducted.

# Boehringer Ingelheim BI Trial No.: 1368-0098

c40061625-02 Clinical Trial Protocol

As briefly described in Section 4.1.3, the medication will be assigned

Page 64 of 177

Proprietary confidential information © 2023 Boehringer Ingelheim International GmbH or one or more of its affiliated companies

There are no special requirements on drug administration in relation to meals. Administration of study medication should occur after ECG and after blood sampling.
If available, a pharmacist should prepare the study medication. The so-called four eye principle (two-person rule) should be applied for preparation (e.g. choosing the correct vials with the correct medication number) and administration of trial medication.
(Visits 2, 3, 4, and 5 Trial participants will receive spesolimab or matching placebo. The administration of the trial medication will be done by a trained health care professional. Detailed instructions for the preparation of the and the are provided in the ISF. The administration of doses will be done at site.
(Visit 6 to 31  Trial participants will receive of spesolimab or matching placebo.
provided in the ISF.
is allowed.
Monitoring after administration  Trial participants should be closely monitored for AEs, including signs and symptoms of hypersensitivity reactions, for 2 hours after the first dose of trial drug administered at Day 1 (Visit 2) and 1 hour following all other doses of trial drug. Study personnel should observe the should also ask trial participants about itching, dizziness or shortness of breath. Trial participants should be advised to notify site personnel in case they experience redness, swelling or other changes at the separate itching all over or a feeling of being swollen, dizzy or short of breath, they should seek emergency medical attention immediately and notify site personnel, see Section 5.2.6 about AE reporting.
In case of safety concerns, e.g. due to it is in the discretion of the investigator or his/her designee to adapt the and - provided no further safety concern exist - Further, based on medical judgment he/she will provide medications such as steroids, etc, as needed (see Section 4.2.1 for handling of are also provided in the "Instructions for Pharmacist" document placed in the ISF. Pre-medications for further might be considered and will be agreed on between investigator and BI clinical monitor.

c40061625-02

Clinical Trial Protocol

Page 65 of 177

Proprietary confidential information © 2023 Boehringer Ingelheim International GmbH or one or more of its affiliated companies

Dose modifications or dose adjustments are not permitted except as per protocol (see from of Part 1 (implemented by IRT if applicable Section 3.1 possible as per allocated blind treatment group). In exceptional cases of missed or delayed visits, if any of these visits have to be rescheduled, the date of subsequent visit should be calculated from baseline (Visit 2). After Visit 5 in case of delayed visits, IMP can be administered with a minimum interval of 7 days from the next dose, only after discussion and approval from the sponsor. Placebo controlled period of Part 1 (Up to Visit 14 Table 4.1.5: 1 Administration of trial drug Overview of treatment course from Visit 15 up to Visit 31 Table 4.1.5: 2 Administration of trial drug From Visit 23 on, trial participants will continue to receive the previously assigned dosing regimen until the results of primary analysis are available. Upon availability of the Phase IIb (Part 1) primary analysis efficacy and safety results, the dosing regimen may be adapted from Visit 23

Page 66 of 177

Proprietary confidential information © 2023 Boehringer Ingelheim International GmbH or one or more of its affiliated companies

[figure not shown]
[figure not shown]

Table 4.1.5: 4 Dosage and treatment schedule for the

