#### **1.4.2** Risks

No other IL-36 receptor antagonist is currently approved, that would provide further information on identified risks in molecules of this class. The knowledge of the safety and risk profile of compounds in this class is still considered limited. However, the safety profile of spesolimab is considered acceptable based on available data from completed trials.

In order to protect the trial participant's safety during conduct of this trial, an independent Data Monitoring Committee (DMC) will periodically review clinical trial safety data. For details, please see Section 8.7. In addition to the AE tracking, planned interim analysis at of Part 1 of the trial will also contribute to the monitoring of any safety signal (see Section 7.2.8).

For potential risks, Table 1.4.2: 1 lists the possible risks for spesolimab as well as theoretical risks derived from general safety considerations of immunomodulatory drugs and from this trial specific procedures. For details on treatment-related risks, refer to Section 1.2 and IB [c03320877-11].

Page 32 of 177

Table 1.4.2: 1 Overview of trial-related and potential risks

Possible or known risks of clinical relevance for this trial	Summary of data, rationale for the risk	Mitigation strategy
Systemic hypersensitivity reaction	After administration of any biologic agent or protein, there is a possibility of occurrence of immediate (such as anaphylaxis) or delayed (such as drug reaction with eosinophilia and systemic symptoms) adverse immune reactions.	Patients with a history of allergy/hypersensitivity to the systemically administered trial medication agent or its excipients are excluded from the trial.  In case of systemic hypersensitivity reactions including anaphylactic reaction emerging during or after administration of trial medication, the investigator should consider in accordance with severity of the reaction and local standard of care to interrupt and treat the condition.
		Systemic hypersensitivity reaction is defined as an adverse event of special interest (AESI); see Section 5.2.6.1.4. It is subject to close monitoring and investigators are requested to assess these conditions using the criteria discussed in the statement paper from Sampson HA [R11-4890].

Page 33 of 177

Proprietary confidential information © 2023 Boehringer Ingelheim International GmbH or one or more of its affiliated companies

Table 1.4.2: 1 Overview of trial-related and potential risks (cont.)

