resulting in paraesthesia, reduced sensibility, and/or pain for an indefinite period.	mark) at the puncture site. Furthermore, there is a small risk of lightheadedness and/or fainting. In rare cases, the puncture site can also become infected, or nerves may be damaged, inducing long-lasting abnormal sensations (paresthesia), impaired sensation of touch and persistent pain.	These risks will be addressed by careful safety monitoring and risk mitigation measures such as  (a) pressure on the puncture site for approximately 5 minutes after the needle extraction, is recommended.  (b) close clinical monitoring for AEs.  (c) selection of experienced sites and site staff.  (d) safety recommendations provided in laboratory	
Skin biopsy	Can cause local bruising, inflammation, nerve damage and pain.	manual.  These risks will be addressed by careful safety monitoring and risk mitigation measures such as  (a) close clinical monitoring for AEs.  (b) selection of experienced sites and site-staff.  (c) staff training.	

Page 37 of 177

Proprietary confidential information © 2023 Boehringer Ingelheim International GmbH or one or more of its affiliated companies

Table 1.4.2: 1 Overview of trial-related and potential risks (cont.)

Other risks		
Administration of placebo	If the trial participant is randomised to receive a placebo, the participant's condition could get worse during the trial.	The placebo control is required to control for investigator bias and/or beneficial effects of being in a clinical trial. The rationale for switching placebo trial participants to active treatment at Visit 14 is to give these trial participants the opportunity to receive active investigational medicinal product (IMP) treatment from that visit.
		The use of rescue medication is foreseen in this trial for participants experiencing a worsening of their HS condition; see Section 4.2.3 .

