#### Screening and randomisation After signing the informed consent, trial participants will enter the screening period for up to 28 days, and if all eligibility criteria are met, trial participants will be randomised in a ratio to either active group, including high dose, medium dose, and low dose group, or placebo group The randomisation will be stratified for and baseline For stratification, the details are described in Section 7.4. At least approximately participants from population (meaning a corresponding and a maximum of approximately participants from population (meaning a corresponding are planned to be randomised, respectively. These participants who were might have had a primary or a secondary failure of previously Primary failure of is defined as lack of efficacy after at least 3 months of treatment with an agent (patients who never responded), and secondary failure is defined as loss of clinical efficacy in a trial participant after initial response to an agent (patients who initially responded but then relapsed). Additionally, might have due to AE or stopped for other reason. Approximately participants with baseline and participants with baseline are planned to be randomised, respectively. No stratification beyond those prior described will be applied for the trial participants. Study in the Flowchart represents the is used for Day 1.

Boehringer Ingelheim BI Trial No.: 1368-0098

c40061625-02 Clinical Trial Protocol Page 47 of 177

Proprietary confidential information © 2023 Boehringer Ingelheim International GmbH or one or more of its affiliated companies

Treatment phase Once randomised, trial participants will start a treatment period of Administration of treatment will be up to The final assessment of treatment effect will be on (EoT visit).
For the first according to the assigned dose group, trial participants will be administered an initial dose of spesolimab high dose group], at Visit 2 Visit 3 Visit 4 , and Visit 5 or matching placebo.  From Visit 6 to Visit 9 (both inclusive), trial participants will be administered a group], or medium dose group], or medium dose group], or medium dose group], or matching placebo. For trial participants initially randomised to spesolimab group, from Visit 10 to Visit 31 (both inclusive), the participants will be administered a dose of spesolimab: either (high and medium dose group) or low dose group)  [Indicate the assigned dose group] according to the assigned dose group).

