From Visit 14 , there is an option of increasing the dose to the maximum subcutaneous dose of applied to low dose treatment group participants only, via IRT in a blinded manner) if they have compared to baseline and the investigator agrees with the dose increase.
For trial participants initially randomised to placebo group, from Visit 10 to Visit 13 (both inclusive), the participants will be administered a matching placebo Visit 14 to Visit 31 (both inclusive), the participants will be dose of spesolimab
From Visit 23 on, trial participants will continue to receive the assigned dosing regimen, at least until the results of are available. Upon availability of the Phase IIb (Part 1) primary analysis efficacy and safety results, the dosing regimen may be adapted from Visit 23. For more detailed drug assignment and administration of doses for each trial participant, please see Section 4.1.5.
Follow-up phase and end of study  Trial participants completing EoT visit of the study may roll over to an if they agree and meet the eligibility criteria. These trial participants are not required to complete a safety follow-up period, and their EoT visit will be considered also their end of study (EoS) visit, which is the
Trial participants, who permanently discontinue trial drug earlier than Visit 31 do not qualify to enter the LTE trial for any other reason, will be invited to do the EoT visit instead of the next planned visit and will then enter a safety follow-up period

BI Trial No.: 1368-0098

c40061625-02 Clinical Trial Protocol Page 48 of 177

Proprietary confidential information © 2023 Boehringer Ingelheim International GmbH or one or more of its affiliated companies

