# The following are considered as AESIs:

Systemic hypersensitivity including infusion reaction and anaphylactic reaction
Any suspicion of severe infusion reaction systemic/hypersensitivity reaction and of any
potential cases of anaphylaxis should be defined and assessed using the criteria discussed in
the statement paper from Sampson HA (Appendix 10.20 [R11-4890]), see Section 4.2.1 for
"Other treatments and emergency procedures".

Severe infections (according to CTCAE grading in Section 15 of the ISF) (See Section 4.2.1 for "Other treatments and emergency procedures")

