6. GENERAL ANALYSIS DEFINITIONS

6.1 TREATMENT(S)

Part 1 (Phase IIb)

Date: 07-08-2024, Version 1.0

The analysis periods are defined relative to the day of randomization (Day 1) in Table 6.1:1:

Table 6.1: 1 Flow chart of analysis periods of the study according to randomized treatment

Study analysis period	Description	Start (included)	End (included)
Screening period	Screening	Earliest of (Date of informed consent, first screening procedure)	Date/time of start of the first study dose minus 1 minute.
Loading period (from Day 1 to	On- treatment period	Date/time of start of the first study loading dose (Day 1)	Earliest of i) Date/time of start of the first maintenance dose minus1 minute; ii) Date of end of last loading dose + 112 days at 11:59 p.m. if patient early discontinued study treatment before visit; iii) last contact date on End of Study page at 11:59 p.m.
Maintenance period I (from to Week 8)		Date/time of start of the first maintenance dose for visit (if applicable)	Earliest of i) Date/time of start of the study maintenance dose for Week 8 visit minus 1minute; ii) Date of end of last maintenance dose + 112 days at 11:59 p.m. if patient early discontinued study treatment before Week 8 visit; iii) last contact date on End of Study page at 11:59 p.m.
Maintenance period II (from Week 8 to Week 16)		Date/time of start of the study maintenance dose for Week 8 visit (if applicable)	Earliest of i) Date/time of start of the study maintenance dose for Week 16 visit minus 1minute; ii) Date of end of last maintenance dose + 112 days at 11:59 p.m. if patient early discontinued study treatment before Week 16 visit; iii) last contact date on End of Study page at 11:59 p.m.
Maintenance period III (from Week 16 to		Date/time of start of the study maintenance dose for Week 16 visit (if applicable)	Earliest of i) Date/time of the first treatment in OLE trial 1368.0130 minus1 minute if subject is rolled over; ii) Date of end of last maintenance dose + 112 days at 11:59 p.m. if patient early discontinued study treatment; iii) last contact date on End of Study page at 11:59 p.m.
Off-treatment phase ¹ (if applicable)	Off- treatment period	Date of end of last study dose + 113 days at 0:00 a.m.	Latest of i) Date of EOS visit; ii) last contact date on End of Study page at 11:59 p.m.

Proprietary confidential information © 2024 Boehringer Ingelheim International GmbH or one or more of its affiliated companies.

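### In Part 1, placebo participants get the 2-hour hypersensitivity watch after a placebo dose and only 1 hour after their first spesolimab dose at Visit 14

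*Protocol*

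**What the plan says.** Protocol Section 4.1.5 (Monitoring after administration) requires close observation for adverse events, including signs of hypersensitivity, for "2 hours after the first dose of trial drug administered at Day 1 (Visit 2) and 1 hour following all other doses". The section states that it applies to Part 1 participants, and trial drug there means spesolimab or matching placebo.

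Section 3.1 (Part 1, treatment phase) gives the placebo arm placebo up to Visit 13 and then spesolimab: "Visit 14 to Visit 31 (both inclusive), the participants will be dose of spesolimab" (the gap is a redaction). Table 1.4.2: 1 confirms the switch visit where it gives "The rationale for switching placebo trial participants to active treatment at Visit 14". Exclusion criterion 3 in Section 3.3.3 rules out earlier spesolimab, so Visit 14 is these participants' first exposure.

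On the risk, Table 1.4.2: 1 says "After administration of any biologic agent or protein, there is a possibility of occurrence of immediate (such as anaphylaxis") or delayed immune reactions. Section 5.2.6.1.4 lists "Systemic hypersensitivity including infusion reaction and anaphylactic reaction" among the adverse events of special interest.

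**The concern.** The protocol treats an immediate immune reaction as a risk of giving a biologic and asks for a longer watch at one dose only, the first. For the active arms that dose is the first antibody exposure. For the placebo arm it is not: the extended period follows an injection or infusion with no antibody, and the real first exposure gets the shorter period.

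The stake is participant safety. A reaction that begins more than an hour after the Visit 14 dose would be more likely to begin after the participant has left the site. No efficacy estimate or error rate is affected.

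**Working it through.** **Rule applied to each arm.** The observation rule comes from Section 4.1.5 and the dosing sequence from Section 3.1.

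| Arm | Visit 2 dose | First spesolimab | Observation at first spesolimab |
|---|---|---|---|
| High, medium, low | spesolimab | Visit 2 | 2 h |
| Placebo | placebo | Visit 14 | 1 h |

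The difference at first antibody exposure is 2 − 1 = 1 hour.

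**Is there a Visit 14 rule elsewhere?** None is readable. Section 5.2.2 adds vital signs at about 60 minutes for the later type of administration, but only at Visits 6 and 7, which are also placebo doses in this arm. Section 1.4.2 refers monitoring for reactions to handling instructions in the Investigator Site File, which are not part of the documents. Tables 4.1.5: 1 to 4 are redacted.

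**Why does Visit 2 get 2 hours?** The protocol gives no reason. Section 3.1 places Visit 2 in an initial phase with Visits 3, 4 and 5 ("trial participants will be administered an initial dose of spesolimab high dose group], at Visit 2" begins that list), yet Visits 3 to 5 get 1 hour. Belonging to the initial phase is therefore not enough to earn 2 hours. Being first is the explanation that best fits the readable text.

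**How many participants?** The allocation ratio is redacted, so it is inferred from the design-stage contrasts in SAP Table 7.4: 2. With equal arms and doses in the ratio 0 : 1 : 2 : 4, the mean dose is 7/4 = 1.75. The linear contrast is then (1.75, 0.75, −0.25, −2.25)/√8.75 = (0.592, 0.254, −0.085, −0.761), which matches the printed row. That row alone does not fix the allocation, because the dose ratios are also unknown. Fitting the linear, exponential, Emax and sigmoid Emax rows together, with dose ratios and shape parameters free, equal allocation reproduces every coefficient to within 0.001. Each of nine unequal allocations tried (for example 2:1:1:1, 1:2:2:2 and 2:2:3:3) misses at least one coefficient by more than 0.01.

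A 25% placebo share follows. If 10% to 30% of that arm leave before Visit 14 (an assumption), the affected share of those randomised is 25% × 0.9 = 22.5% down to 25% × 0.7 = 17.5%.

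**Observation time, now and with 2 hours at Visit 14.** Section 6.2.2 has treatment running from Visit 2 to Visit 31. Assume one dose per visit.

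| Span | Doses | Now | With the change |
|---|---|---|---|
| Visits 2–31 | 30 | 2 + 29 × 1 = 31 h | 2 + 2 + 28 × 1 = 32 h |
| Visits 2–14 | 13 | 2 + 12 × 1 = 14 h | 2 + 2 + 11 × 1 = 15 h |

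The increase over the whole schedule is 1/31 = 3.2%.

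**The case against.** The strongest reply is that the two doses are not alike. SAP Table 6.1: 1 dates the loading period from "Date/time of start of the first study loading dose (Day 1"), and Protocol Sections 3.3.4.1 and 4.2.1 describe stopping an infusion and restarting it more slowly. From Visit 14, Section 3.1 speaks of an "option of increasing the dose to the maximum subcutaneous dose of" (the amount is redacted), so the Visit 14 dose appears to be subcutaneous and belongs to the maintenance phase. The 2 hours may have been meant for a first infusion or first loading dose, and the 1-hour period at Visits 3 to 5 fits that reading too. Section 5.2.2 also varies vital-sign timing by type of administration, and its added check at Visits 6 and 7 ends at about 60 minutes, the window that 1 hour covers.

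This stands as a limit on confidence. The readable text cannot separate first dose from first infusion. It does not remove the point, because on either reading nothing extra is readable at the placebo arm's first exposure to the antibody.

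Three further objections are fair:

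- The redactions and the site file could hold a Visit 14 rule. If so, the sponsor need only point to it.
- No harm is shown. Besides the hour of observation and the symptom questions, participants are told when to seek emergency care, emergency procedures exist, and a data monitoring committee reviews safety.
- Most people who would stay the extra hour do not need it. On a 25% placebo share, about three quarters at Visit 14 come from the active arms and have already had 12 planned dosing visits with spesolimab (Visits 2 to 13). That is the price of keeping the blind.

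**Conclusion.** The point holds as a low-cost precaution, with medium confidence. As written, the placebo arm has its 2-hour observation after placebo and 1 hour at its first spesolimab dose, a shortfall of 1 hour against the active arms. This follows directly from Sections 3.1 and 4.1.5 and does not depend on the allocation ratio.

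The number affected does rest on assumptions: a 25% placebo share inferred from the SAP contrasts, and the assumed dropout, giving 17.5% to 22.5% of those randomised. That range counts people covered by the rule; it is not a reaction rate. The documents do not show that reactions occur between 60 and 120 minutes after dosing, so the benefit of the second hour cannot be sized. No claim is made for Part 2, because Section 4.1.5 is to be amended before it starts.

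**What to change.** Amend Section 4.1.5 so that observation lasts 2 hours after the Visit 2 dose and after the Visit 14 dose, in all arms, and 1 hour after every other dose. It must apply to all arms, because a longer stay for the placebo arm alone would reveal the allocation. If the site-file instructions or the redacted tables already require this, a cross-reference in Section 4.1.5 is enough.

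The cost is one extra hour for each participant who reaches Visit 14. The Flowchart footnote does not list Visit 14 among the visits that may be done at home, so trained staff are already present, and no new procedure or data item is needed.
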